5.6 Procedure for Breaking the Blind

Unblinding a subject's treatment assignment in a double-blind, controlled trial should never be undertaken lightly as it can introduce bias in assessment of safety or efficacy. However, in circumstances where immediate knowledge of treatment assignment will meaningfully influence the current or future management of potentially serious AEs, breaking the blind may be appropriate.

Unless the need for unblinding is urgent and obvious, the investigator is encouraged to contact the sponsor/Clinical Research Organization (CRO) medical advisor to discuss their rationale for unblinding. However, to prevent delays to the investigator or medical personnel responding to a potentially emergent situation, unblinding of IMP will not be dependent upon the investigator receiving approval from the sponsor/CRO medical advisor (ie, the investigator will be able to obtain the code break information independent of the sponsor/CRO medical advisor). The investigator must contact the sponsor/CRO medical advisor by telephone or e-mail with an explanation of the need for opening the treatment assignment code within 24 hours of opening the code. If the blind is broken, the Clinical Safety and Pharmacovigilance department must be notified immediately (see the cover page of this protocol for contact information). Documentation of breaking the blind should be recorded in the subject's medical record with the date and time the blind was broken and the names of the personnel involved. Once the blind is broken for a subject, that subject may not reinitiate treatment with the IMP.

5.7 Follow-up of Adverse Events

For this trial, information on AEs will be collected from the signature of the informed consent until 14 days after the last dose of IMP has been administered or until 7 days in subjects who discontinued prior to randomization. Follow-up of AEs is described below.

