^cAny subject who discontinues IMP during Phase A will enter the Follow-up period and then be followed every 6 months through Phase A. The 14 day follow-up visit is a telephone contact only, a clinic visit is not required. Subjects who do not complete Phase A on treatment are not eligible to enter Phase B.

^dAn assessment of vital status will be conducted on subjects who terminate IMP prior to the Phase A Month 12 visit and do not agree to additional safety follow-up but do not withdraw consent for continued telephone contact. See [Section 3.7.4.8](#).

^eADPKD genetic history to be collected if available, although it is not specifically required.

^fA subject who reaches Stage 5 (both in pubic hair and genitalia) does not need to continue with Tanner Staging.

^gMRI/ultrasound imaging: The baseline imaging used must be the same imaging used throughout the trial (Phase A and Phase B). It is recommended that subjects have their imaging done on the same day as the clinic visit; however imaging can be performed up to 30 days prior to the scheduled visit. The subject should be on IMP for 30 consecutive days prior to imaging (except screening). MRI/ultrasound is not required at the EoTx visit.

^hRenal pelvic assessments will be done using ultrasound. The Month 1 assessment can be performed at any scheduled visit between Month 1 and Month 3 but cannot be conducted until 30 days after the subject has started IMP, see [Section 3.7.4.5](#).

ⁱVital signs at each visit include seated heart rate and blood pressure (systolic and diastolic). Temperature will be collected only at the Phase A baseline visit.

^jBody weight should be measured post-void. Growth percentile is not required at the baseline, Wk 1 and M1 visits. Body weight is not required at the Wk 1 and M1 visits. .

^kCentral laboratory serum laboratory tests will be performed for all visits (only monthly safety labs may be collected at a local laboratory). Fasting is required at the screening visit. Fasting is recommended for all other visits, but is not required. Upon request, if clinically indicated and approved by the medical monitor, subjects may have the following evaluations in addition to the protocol-specified chemistry panel: serum calcium, phosphorus, parathyroid hormone, vitamin D, and bicarbonate levels.

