3.7.1.4 Follow-up Period

All subjects will be seen for a follow-up visit after they have discontinued from IMP. Subjects who discontinue IMP but continue to be followed for safety will complete the 7-day post last dose follow-up visit.

3.7.1.4.1 7 Days Post Last Dose Visit (+ 2 days)

All subjects will be seen in the clinic 7 days (+ 2) after their last dose of IMP. The following assessments will be completed:

Protocol 156-12-298

- 1) Laboratory samples for liver function tests will be collected for analysis at the central laboratory. Liver function tests may be limited to include AST and ALT only, as clinically appropriate.
- 2) Concomitant medications will be recorded.
- 3) Adverse events will be recorded.

3.7.1.4.2 14 Days Post Last Dose Telephone Call (+ 2 days)

Subjects or their parent(s)/legal guardian(s) or legally acceptable representative(s) will be contacted via telephone or will be asked to come back to the clinic for a visit at 14 (+ 2) days post last dose to assess any new or ongoing AEs, and to collect information on any medications administered since the last visit. Ongoing follow-up may be required after a subject's trial completion for health status before the analysis of all trial results is completed.

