3.8.3.2 Treatment Discontinuation

After randomization, a subject may stop treatment permanently for a variety of reasons. Treatment discontinuations may be initiated by a subject who is not satisfied with treatment or may become medically necessary due to AEs, required treatment with a disallowed medication or therapy, or other issues, as determined by the investigator. However, each investigator must comprehensively review the circumstances and offer the subject options for continued treatment to the degree possible as described in [Section 3.8.3.4](#).

Subjects who have sustained electrolyte excursions (eg. increased serum sodium) that are considered clinically significant by the investigator and that are not able to be resolved by increasing the subject's daily water intake should be discontinued from treatment.

A subject who discontinues treatment will be recorded as an IMP discontinuation on the eCRF. They will have an EoTx visit, which should be scheduled as soon as possible after

Protocol 156-12-298

the subject's last dose of IMP to conduct the assessments defined in the Schedule of Assessments, [Table 3.7-1](#) for Phase A and [Table 3.7-2](#) for Phase B.

Subjects who discontinue IMP during Phase A, will have safety laboratory tests (including LFTs) at the 7-day posttreatment follow-up visit (see [Section 3.7.1.4.1](#)), and then will be followed every 6 months through Phase A (see Schedule of Assessments [Table 3.7-1](#)). Collection of an MRI/Ultrasound TKV measurement at the Phase A Month 12 visit will be encouraged regardless of whether the subject continues on IMP.

Subjects who discontinue IMP during Phase B, will have safety laboratory tests (including LFTs) at the 7-day posttreatment follow-up visit (see [Section 3.7.1.4.1](#)), and then will be followed every 6 months through Phase B (see Schedule of Assessments [Table 3.7-2](#)). Collection of an MRI/Ultrasound TKV measurement at the Phase B Month 12 and Phase B Month 24 visit will be encouraged regardless of whether the subject continues on IMP.

Subjects whose consents are completely withdrawn will be discontinued from the trial. These subjects' vital statuses will be collected if possible at the time points defined in [Section 3.7.4.8](#).

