- Any subject reporting an AE of special interest (eg, skin neoplasms or glaucoma)
- Pregnancies are also defined as IREs. Although normal pregnancy is not an AE, it will mandate IMP discontinuation and must be reported on an IRE form to the sponsor. Pregnancy will only be documented on the AE eCRF page if there is an abnormality or complication.
- Additionally, in the European Union, events involving overdose, misuse, and abuse as well as reported lack of efficacy must also be reported as IREs.

Clinical Laboratory Test Value Changes: It is the investigator's responsibility to review the results of all laboratory tests as they become available. This review will be documented by the investigator in source documents. For each abnormal laboratory test result, the investigator needs to ascertain if this is an abnormal (ie, clinically significant) change from baseline for that individual subject. This determination, however, does not necessarily need to be made the first time an abnormal value is observed. The investigator may repeat the laboratory test or request additional tests to verify the results of the original laboratory tests. If this laboratory value is considered medically relevant by the investigator (subject is symptomatic, requiring corrective treatment or further evaluation), or if the laboratory value leads to discontinuation, and/or fulfills a seriousness criterion, this is considered an AE.

Severity: Adverse events will be graded on a 3-point scale and reported as indicated on the eCRF. The intensity of an adverse experience is defined as follows:

1 = Mild: Discomfort noticed, but no disruption to daily activity.

2 = Moderate: Discomfort sufficient to reduce or affect normal daily activity.

3 = Severe: Inability to work or perform normal daily activity.

IMP Causality: Assessment of causal relationship of an AE to the use of the IMP is defined as follows:

Related: There is a reasonable possibility of a temporal and causal relationship between the IMP and the AE.

Not Related: There is no temporal or causal relationship between the IMP and the AE.

Protocol 156-12-298

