A urine and/or serum pregnancy test for human chorionic gonadotropin will be performed at screening on all females of childbearing potential. If a urine test is performed and is positive, the investigator will follow-up with a confirmatory serum test.

During the trial, all females of childbearing potential should be instructed to contact the investigator immediately if they suspect they might be pregnant (eg, missed or late menstrual cycle).

If a subject is suspected to be pregnant before she receives IMP, the IMP administration must be withheld until the results of serum pregnancy tests are available. If the pregnancy is confirmed, the subject must not receive the IMP and must not be enrolled in the trial. If pregnancy is suspected while the subject is taking IMP, the IMP must be withheld immediately (if reasonable, taking into consideration any potential withdrawal risks) until the result of the pregnancy test is known. If pregnancy is confirmed, the IMP will be permanently discontinued in an appropriate manner (eg, dose tapering if necessary for subject safety) and the subject will be withdrawn from the trial.

The investigator must immediately notify the sponsor of any pregnancy associated with IMP exposure during the trial and for 30 days after the last dose of IMP, and record the event on the IRE form and forward it to the sponsor. The sponsor will forward Pregnancy Surveillance Form(s) for monitoring the outcome of the pregnancy.

Protocol required procedures for trial discontinuation and follow-up must be performed on the subject unless contraindicated by pregnancy (eg, x-ray studies). Other appropriate pregnancy follow-up procedures should be considered, if indicated. In addition, the investigator must report to the sponsor, on appropriate Pregnancy Surveillance Form(s), follow-up information regarding the course of the pregnancy, including perinatal and neonatal outcome. Infants will be followed for a minimum of 6 months from the date of birth.

Protocol 156-12-298

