5.7.1 Follow-up of Nonserious Adverse Events

Nonserious AEs that are identified at any time during the trial must be recorded on the AE eCRF page with the current status noted. All nonserious events that are ongoing at the last scheduled contact will be recorded as ongoing on the CRF. For any AE having been identified throughout the trial, during analysis, additional relevant medical history information may be requested to further ascertain causality (including, but not limited to, information such as risk-related behavior, family history and occupation).

The investigator will follow all AEs until the events are resolved, stabilized, or the subject is lost to follow-up. Resolution means that the subject has returned to the

Protocol 156-12-298

baseline state of health and stabilized means that the investigator does not expect any further improvement or worsening of the subject's condition.

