9.2 Adverse Events

All adverse events (AE) will be coded by MedDRA System Organ Class (SOC) and Preferred Term (PT). A treatment-emergent AE (TEAE) is defined as an AE which starts after start of trial medication), or an AE continues from baseline of the specific phase and becomes serious, worsening, trial drug-related or results in death, discontinuation, interruption or reduction of trial medication during this phase. The incidences of the following treatment-emergent adverse events (TEAEs) will be summarized by treatment groups:

- TEAEs by severity
- Potentially drug-related TEAEs
- TEAEs with an outcome of death
- Serious TEAEs
- Discontinuations due to TEAEs

Incidences of AEs above will be tabulated by treatment for Phase A safety dataset and Phase B safety dataset, respectively.

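### For subjects who stop treatment but stay in follow-up, the protocol's adverse-event recording rules contradict each other, and the SAP sets no end to the treatment-emergent window

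*Protocol*

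**What the plan says.** **End of collection.** Protocol section 5.7 states that "information on AEs will be collected from the signature of the informed consent until 14 days after the last dose of IMP has been administered". It then refers to the subsections below it for follow-up.

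**Nonserious events.** Section 5.7.1 sets a different limit: "Nonserious AEs that are identified at any time during the trial must be recorded on the AE eCRF page". Section 5.2 likewise requires every AE that a subject reports to be recorded, and it gives no closing date.

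**Follow-up after stopping.** A footnote to the Phase A schedule (Table 3.7-1) says that a "subject who discontinues IMP during Phase A will enter the Follow-up period and then be followed every 6 months through Phase A". Section 3.8.3.2 repeats this and gives the same rule for Phase B. Section 7.3 adds that subjects who stop treatment are encouraged to return for their remaining visits.

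**Visit lists.** AE recording is listed at Phase A Month 6 (3.7.1.1.7) and Month 12 (3.7.1.1.8), at Phase B Months 6, 12 and 18 (3.7.1.2.4) and at Phase B Month 24 (3.7.1.2.6). None of these excepts subjects who are off IMP.

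**Serious and special-interest events.** Section 5.7.2 covers SAEs found or still ongoing at the last scheduled contact, including new ones. Section 5.1 makes any SAE immediately reportable, and also "Any subject reporting an AE of special interest (eg, skin neoplasms or glaucoma"). Section 5.3 requires such reports within 24 hours of awareness.

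**Analysis.** SAP section 9.2 reads: "A treatment-emergent AE (TEAE) is defined as an AE which starts after start of trial medication". A second limb covers AEs that continue from the baseline of a phase and worsen, or otherwise qualify, during that phase. The SAP tabulates AEs separately for the Phase A and Phase B safety sets.

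**The concern.** The primary objective is long-term safety, so the AE tables are the main output of the trial. For an early stopper, sections 5.7 and 5.7.1 give opposite instructions for every visit more than 14 days after the last dose, and nothing says which one governs. A site that follows 5.7 leaves a late nonserious AE out of the database. A site that follows 5.7.1 and the visit list enters it. The count of such events then depends partly on how each site read the protocol.

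The SAP adds a second problem for the events that are entered. With no end to the first limb of the TEAE definition, an event that starts eleven months after a subject's last dose is tabulated beside one that starts on Day 3. The tables would mix on-treatment and off-treatment experience, and a reader could not separate them.

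**Working it through.** The plan states no figure for this point. It is a descriptive trial with no power calculation, and no discontinuation or AE rate is given. The check is a comparison of passages, day counts, and an illustration on assumed rates.

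**Step 1: passages side by side.** Take a Phase A subject who stops on Day 28 and reports a new nonserious AE at Month 6.
- Section 5.7: collection closed on Day 28 + 14 = Day 42, so the event is not collected.
- Section 5.7.1: the event was identified during the trial, so it is recorded.
- Section 3.7.1.1.7 (Month 6 list): AEs are recorded, with no exception for subjects off IMP.
- SAP 9.2: if recorded, the event started after first dose and is a TEAE. The phase wording in the second limb does not reach it.

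**Step 2: days on which the rules disagree.** Days = phase end − stop day − 14. Phase A ends on Day 365 (Table 3.7-1). Phase B is taken as 730 days, an assumption for 24 months.

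| Phase | Stop day | Days | Share of phase |
|---|---|---|---|
| A | 7 | 365 − 7 − 14 = 344 | 94% |
| A | 28 | 365 − 28 − 14 = 323 | 88% |
| A | 182 | 365 − 182 − 14 = 169 | 46% |
| B | 28 | 730 − 28 − 14 = 688 | 94% |
| B | 182 | 730 − 182 − 14 = 534 | 73% |
| B | 365 | 730 − 365 − 14 = 351 | 48% |

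These figures show exposure to the ambiguity. They do not measure bias.

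**Step 3: illustration on assumed rates.** Let r be the 12-month risk of at least one event of a given type and q the share of an arm that stops early. Assume a constant hazard h = −ln(1 − r)/365, unchanged by stopping, and stop days t uniform over 1 to 365. With full capture and no cut-off, incidence is r. With everything after last dose + 14 days left out, it is (1 − q) × r + q × m, where m is the mean over t of 1 − exp(−h × min(365, t + 14)). An arm has 30 subjects (60 at 1:1).

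| r | q | m | With cut-off | No cut-off | Difference | Subjects of 30 |
|---|---|---|---|---|---|---|
| 10% | 5% | 0.0548 | 9.8% | 10.0% | 0.2 points | 0.1 |
| 30% | 20% | 0.1705 | 27.4% | 30.0% | 2.6 points | 0.8 |
| 50% | 30% | 0.2980 | 43.9% | 50.0% | 6.1 points | 1.8 |

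Middle row: 0.8 × 0.30 + 0.2 × 0.1705 = 0.2741. Each row compares the two extremes, with every site reading the rules one way or the other. A mixture of sites falls between them.

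**Step 4: who is affected.** Only subjects who stop IMP and remain in follow-up. A subject who goes directly from Phase A to Phase B on IMP has no such gap.

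**The case against.** The strongest reply is that this is a wording conflict with little consequence. Section 5.7 sends the reader to its subsections. Section 5.7.2 picks up SAEs at the last scheduled contact, which for a followed early stopper is the Month 12 or Month 24 visit. Special-interest events must be reported within 24 hours with no 14-day limit stated. If sites applied 5.7 strictly, almost no late nonserious event would reach the database, so the open TEAE definition would have little to act on. In the middle case of the illustration the shift is under one subject per arm. All of this stands. It confines the collection problem to late nonserious events and makes the TEAE problem conditional on those or other late events being recorded. It does not resolve the contradiction, because the visit lists invite sites to record.

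Three stronger readings are tempting, and the documents do not support them.

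- **Late safety data lost altogether.** The day counts might suggest that nearly all AEs after stopping go uncollected. They do not describe SAEs or special-interest events, for the reasons above.
- **Bias between arms.** Section 1.3 says that aquaretic reactions are the ones most likely to limit continued therapy, so a reader might infer more stopping on tolvaptan and hence uneven capture by arm. That passage describes adult experience. No stopping rate by arm is given, and Phase A sites are blinded.
- **A pregnancy gap.** Section 5.5 requires notification of "any pregnancy associated with IMP exposure during the trial and for 30 days after the last dose of IMP", which outlasts the 14-day AE window. This is no contradiction: pregnancy is an immediately reportable event with its own form, and a normal pregnancy is not an AE (5.1). A pregnancy test is scheduled at Month 12, Month 24 or end of treatment, just after the last dose. Subjects must also contact the investigator at once if they suspect pregnancy.

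**Conclusion.** The point holds in a limited form. For early stoppers who remain in follow-up, section 5.7 conflicts with section 5.7.1 and the visit lists, so capture of late nonserious AEs can depend on the site. Separately, the first limb of the SAP's TEAE definition has no end, so any late event that is recorded, of whatever seriousness, counts as treatment-emergent.

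The disputed interval runs from 46% to 94% of Phase A for stops between Day 182 and Day 7. The effect on incidence cannot be computed from the documents. On the assumed rates it runs from 0.2 to 6.1 points per arm, at most about 1.8 of 30 subjects. That range rests on a constant hazard, uniform stop times, and stopping shares of 5% to 30%, none of which the plan supplies. No claim about a difference between arms is supported. The point is worth correcting because safety is the primary objective and the change is cheap. It does not threaten the trial.

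**What to change.** **Protocol 5.7.** Reconcile it with 5.7.1 and the visit lists in one sentence: in subjects who stop IMP but stay in the trial, AEs are recorded through their last scheduled contact, at the 6-monthly visits already planned. The Amendment 2 summary says that all Phase A assessments were complete by then, so this can now change collection in Phase B only. The existing day-14 contact should stay where it is, because it closes the 14-day window for subjects with no later visit.

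**SAP 9.2.** Close the TEAE window for each phase at a stated interval after that phase's last dose (for example 14 days, to match 5.7), or at the first Phase B dose if that comes earlier. Tabulate later events separately as post-treatment. SAP section 6.3 already splits concomitant medications into those used during and after the medication period, so the AE tables would follow an existing convention. This change serves both phases.

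**Cost.** Wording in two sections, slightly more AE entry at existing visits, and one extra table. For Phase A, the report should say that late nonserious AEs in off-treatment subjects were collected under conflicting rules.

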5.7.1 Follow-up of Nonserious Adverse Events

Nonserious AEs that are identified at any time during the trial must be recorded on the AE eCRF page with the current status noted. All nonserious events that are ongoing at the last scheduled contact will be recorded as ongoing on the CRF. For any AE having been identified throughout the trial, during analysis, additional relevant medical history information may be requested to further ascertain causality (including, but not limited to, information such as risk-related behavior, family history and occupation).

The investigator will follow all AEs until the events are resolved, stabilized, or the subject is lost to follow-up. Resolution means that the subject has returned to the

Protocol 156-12-298

baseline state of health and stabilized means that the investigator does not expect any further improvement or worsening of the subject's condition.

